14.0 ETHICAL CONSIDERATIONS

The rights, safety and wellbeing of clinical study subjects shall be protected consistent with the ethical principles outlined in the Declaration of Helsinki. This shall be understood, observed and applied at every step in this clinical investigation.

It is expected that all parties will share in the responsibility for ethical conduct in accordance with their respective roles in the investigation. The Sponsor and the treating physician shall avoid improper influence or inducement of the patient, study monitor, treating physician or other parties participating in or contributing to the clinical study.

15.0 PROTECTION OF PATIENT CONFIDENTIALITY

At all times throughout the clinical investigation, confidentiality will be observed by all parties involved. All data shall be secured against unauthorized access. Privacy and confidentiality of information about each patient shall be preserved in the reports and in any publication. Each patient participating in this study will be assigned a unique identifier. All data will be tracked, evaluated, and stored using only this unique identifier. See Sec. 16.0 for more details.

The study site will maintain a confidential study patient list (paper or electronic) identifying all enrolled patients. This list will contain the assigned study patient's unique identifier and name. The treating physician bears responsibility for keeping this list confidential. This list will not be provided to the study sponsor and is only to be used at the study center.

Monitors and auditors will have access to the study patient list and other personally identifying information of study patients to ensure that data reported corresponds to the person who signed the ICF and the information contained in the original source documents. Such personal identifying information may include, but is not limited to the patient's name, address, date of birth, gender, race and medical record number.

16.0 DATA COLLECTION

Subject data will be collected in a secure electronic data capture (EDC) system via the internet. All baseline, index procedure and 3-month data will be entered by the study site personnel in the electronic Case Report Forms (eCRFs). A unique subject ID number will be assigned to each subject. Every reasonable effort should be made to complete data entry within 10 business days of data collection. Any discrepancies may be queried during routine monitoring visits. Data monitoring will be performed to verify data accuracy and ensure queries are resolved.

Subject reported outcomes obtained via EDC system are considered to be source documents for this study.

17.0 PROTOCOL DEVIATIONS

A protocol deviation is defined as an event where the Investigator or site personnel did not conduct the trial according to the protocol or the investigator agreement. Deviations must be reported to Aerin Medical regardless of whether medically justifiable, pre-approved, or performed to protect the subject in an

emergency. Examples of deviations that are required to be reported to Aerin Medical include, but not limited to the following:

- Informed Consent Form is not obtained before data collection
- Subjects are enrolled that have not met the eligibility criteria
- Subject misses the 3-month Investigator Visual Assessment Follow-up Visit

Investigators are required to report deviations to Aerin Medical by completing a Protocol Deviation eCRF. The investigator is obliged to comply with IRB procedures and/or local laws for reporting deviations. Aerin Medical shall review reported deviations upon receipt and determine appropriate action and regulatory reporting requirements.

18.0 STUDY SUSPENSION OR EARLY TERMINATION

The study can be discontinued at the discretion of the Sponsor for reasons including, but not limited to, the following:

- Obtaining new scientific knowledge that shows that the study is no longer valid or necessary
- Insufficient recruitment of patients
- Persistent non-compliance with the protocol

If the study is discontinued or suspended prematurely, the Sponsor shall promptly inform all participating study sites and treating physicians / investigational center(s) of the termination or suspension and the reason(s) for this. The IRB/EC shall also be informed promptly and provided with the reason(s) for the termination or suspension by the Sponsor. Regulatory authorities and the personal physicians of the patients may also need to be informed if deemed necessary.

19.0 RESPONSIBILITIES

Aerin Medical Inc. is the manufacturer of the Vivaer[®] ARC Stylus and the Sponsor of this study. The Sponsor has the overall responsibility of the study and will work to ensure compliance with the Investigational Plan, elements of Good Clinical Practice: Consolidated Guidance (ICH, April 1996), signed study agreements and 21 CFR 812.2(b), *Abbreviated Requirements*.

The sponsor will be responsible for, but not limited to, conducting the following tasks:

- Ensuring the treating physicians are trained to the Vivaer[®] ARC Stylus
- Provide appropriate information to treating physicians and clinic staff
- Promptly inform the treating physicians and where applicable any regulatory authorities and Ethics Committees, if the study is prematurely terminated or suspended and the reason for the termination or suspension
- Provide protocol initiation training to include the study protocol, data completion guidelines, and guidelines for obtaining informed consent
- Coordinate ongoing communication with consultants and study sites to resolve any problems concerning the protocol or data collection. Every effort will be made to ensure compliance with the protocol

- Retain ownership of all clinical data generated in this study, and control the use of the data for purposes of regulatory submissions to the US and other regulatory agencies
- Protect patient confidentiality

The Sponsor will be responsible for **maintaining study records** per 21 CFR 812.140(a) and Good Clinical Practice: Consolidated Guidance (ICH, April 1996), Section 4.9.

The Sponsor will allow auditing of their clinical investigation or study procedure(s).

The Sponsor is responsible for maintaining study records for every patient participating in study (including information maintained electronically). The Sponsor will also maintain any **original** source documents from which study-related data are derived, which may include, but are not limited to:

- Notes of phone calls and/or correspondence indicating site's attempts to contact and follow a study patient at the required follow-up time points until such time a subject is determined to be lost-to-follow-up.

The Sponsor must ensure that all study patient records are stored for at least 2 years after the latter of the following two dates: The date on which the investigation is terminated or completed, or the date that the records are no longer required for purposes of this study or a notice of completion of a product development protocol. To avoid error, the site should contact the sponsor prior to the destruction of study records to ensure that they no longer need to be retained. In addition, the sponsor should be contacted if the site is acquired or shuts down so that arrangements can be made for the handling or transfer of study records.

20.0 PUBLICATION POLICIES

The Clinical Trial Agreement (CTA) mutually signed by the Investigator(s) and Aerin Medical, defines and describes the nature of the study agreement. The data and results from the AERWAY study are the sole property of Aerin Medical. Aerin Medical shall have the right to access and use all data and results generated during the clinical investigations. Publication authorship will be established according to International Committee of Medical Journal Editors (ICMJE) guidelines and Aerin Medical policy. Clinical study design will be publicly disclosed on ClinicalTrials.gov, and summary results posted per FDAAA 801 Requirements. Additionally, an Investigator may only publish data generated by this trial in accordance with the terms of the Clinical Trial Agreement.

It is Aerin Medical's intent to encourage and facilitate the publications of scientifically important results, while simultaneously ensuring minimization of duplicative data publication and the priority publications of multi-center results ahead of single-center investigations.

Aerin Medical intends to provide research sites with a standardized AERWAY study report containing aggregated site study data.

1 ABBREVIATIONS

AE – Adverse event

CSR – Clinical study report

FAS – Full Analysis Set

NAO – Nasal airway obstruction

NOSE – Nasal Obstruction Symptom Evaluation

PPS– Per-Protocol Eligible Set

SAP – Statistical analysis plan

VAS – visual analog scale

Statistical Analysis Plan TP900 (AERWAY)

2 INTRODUCTION

The purpose of this statistical analysis plan (SAP) is to prespecify statistical analysis methods for supporting completion of publications and clinical study report (CSR) of TP900 (AERWAY) for the Vivaer product.

The AERWAY postmarket study was primarily designed to generate additional effectiveness evaluations through observational reporting of outcomes measures defined in the protocol. No specific hypotheses or hypothesis tests were defined in the study protocol. This SAP outlines the data summaries, statistical techniques, and analyses that will be used to evaluate the effectiveness and safety measures and to propose subgroup analyses of interest.

Results of analyses performed under this SAP may be included in regulatory submissions, clinical study reports and/or manuscripts. Additional exploratory analyses, which are not defined in this SAP, may be performed to further support the clinical development program. Those additional analyses will be detailed in an amendment to this plan and/or documented in the CSR.

3 STUDY DESIGN

This is a single-arm, nonrandomized, prospective, multicenter postmarket study initiated in 2020 to collect longer-term data up to 36-months postprocedure on the effectiveness of the Vivaer procedure for treatment of nasal airway obstruction (NAO). Planned enrollment was 125 participants at up to 20 sites.

All participants were evaluated in-office prior to treatment and following treatment 3 months. Extended follow-up evaluations have been, or will be conducted remotely by phone at 6, 12, 24, and 36 months.

4 STUDY OBJECTIVES AND ENDPOINTS

The primary objective of this study is to continue to evaluate the effectiveness of the Vivaer ARC Stylus for treating the nasal valve area to improve symptoms in those diagnosed with NAO. Effectiveness is assessed through several outcome measures and endpoints as described in Table 1. Outcome measures are further described in Section 8.

Statistical Analysis Plan TP900 (AERWAY)

Table 1. Objectives and endpoints.

Objective	Outcome measures and Endpoints
Evaluate effectiveness through symptom improvement.	
Nasal Obstruction Symptom Evaluation (NOSE) Scale score:
 
 • Mean and mean change from baseline at the 3-, 6-, 12-, 24-, and 36-month follow-up evaluations. • Distribution of NOSE Scale score severity categories (mild, moderate, severe, extreme) at the 3-, 6-, 12-, 24-, and 36-month follow-up evaluations. • Mean, change from baseline in mean, and response distribution of the 5 components of the NOSE Scale score (nasal congestion, nasal blockage, trouble breathing, trouble sleeping, and getting enough air during exercise) at the 3-, 6-, 12-, 24-, and 36-month follow-up evaluations. • Proportion of responders based on improvement in NOSE Scale score at the 3-, 6-, 12-, 24-, and 36-month follow-up evaluations.
Evaluate effectiveness through participant quality of life (QoL) questionnaire feedback.	
QoL questionnaire
 
 • Item response distributions and means where appropriate, at the 3-, 6-, 12-, 24-, and 36-month follow-up evaluations.
Evaluate safety through the safety profile.	
Adverse events
 
 • Frequency of device-related and procedure-related serious adverse events through the 3-month evaluation • Incidence (type, severity, relatedness) of adverse events overall and by follow-up interval.
Evaluate Other Exploratory Outcome Measures	
Nasal Assessment
 
 • Item response distributions prior to the procedure, immediately after the procedure, and at 3 months after the procedure. 
Visual analog scale (VAS) for pain
 
 • VAS pain score assessed at 3 months. 
Medications
 
Updates to current medications or any new or changed medications at the 3-, 6-, 12-, 24-, and 36-month follow-up evaluations.

5 SAMPLE SIZE

The study was designed to enroll up to 125 participants at up to 20 sites. This was initially a registry-type study for collection of data from a substantial number of participants receiving the Vivaer procedure representing diverse clinics and geographical areas but was implemented as a postmarket single-arm study. No formal power analysis was performed; however, substantially smaller sample sizes were found to be sufficiently powerful in prior

Statistical Analysis Plan TP900 (AERWAY)

studies to draw clinically and statistically meaningful conclusions regarding efficacy and safety of the procedure. The larger sample size in this postmarket study was used to potentially support exploratory subgroup analyses of interest.

6 RANDOMIZATION

This is a single-group, prospective, open-label study and therefore randomization is not applicable.

7 BLINDING

Neither the physicians nor participants were blinded as to treatment.

8 OUTCOME MEASURES

8.1 Nasal Assessment

The target nasal valve area within each nostril was visually examined just prior to the procedure, immediately after the procedure, and at 3 months after the procedure. Observations are categorized as not present, mild, moderate, or severe.

Assessments include:

- Saddle nose deformity
- Bruising around orbital area
- Soreness, pain
- Numbness.

Endoscope required for assessment of:

- Inflammation / generalized redness
- Swelling, edema
- Blanching (postprocedure only)
- Bleeding at anesthetic injection site (not requiring physician intervention)
- Bleeding at treatment site (not requiring physician intervention)
- Nasal obstruction from tissue edema
- Disruption of mucosal flow / crusting
- Evidence of increase in diameter of nasal valve (3 months only).

8.2 NOSE Scale Score

To evaluate the significance of a patient's nasal obstruction both before and after the procedure, this study used the well-known patient-reported NOSE Scale for determining the primary assessment of treatment effectiveness. The NOSE Scale is a validated disease-specific health status instrument used by clinicians to measure the outcome of patients treated for nasal obstruction.¹ The NOSE Scale consists of 5 items, each scored using a 5-point Likert scale to make a total score range of 0 through 100, where higher scores indicate worse obstruction. Severity of symptoms can be classified as mild (range, 5-25), moderate (range, 30-50), severe (range, 55-

Statistical Analysis Plan TP900 (AERWAY)

75), or extreme (range, 80-100) nasal obstruction, based on responses to the NOSE survey.²

Treatment responder based on NOSE Scale improvement

Individual participant success (responder) is defined as at least 1 NOSE Scale class improvement, (eg, going from a score in the severe range (55-75) at baseline to a score in the moderate range (30-50) at the follow-up evaluation), or an improvement (decrease) in NOSE Scale score of 20% or more from baseline to the follow-up time point. Other levels of success (definitions of responder) may also be explored.

8.3 Visual Analog Scale (VAS) for Pain

Perception of pain associated with the procedure was measured using a horizontal 100 mm VAS³ anchored on the left with the words “No Pain” (0) and on the right with the words “Worst Pain Imaginable” (10), was used to measure nasal pain associated with the procedure. Scores are obtained by measuring the distance in millimeters from the left origin of the line (0) to the point indicated with a vertical slash placed by the participant to indicate their current level of pain in and around the nose

8.4 Participant Quality of Life Assessment

The QoL questionnaire consists of 4 parts (Appendix A). The first part has 24 items and asks the participant to rate how much of a problem various symptoms and potential effects of their nasal obstruction present to their quality of life at the time of taking the survey relative to the time prior to having the Vivaer procedure. A 6-point ordered rating scale is used with descriptors:

- No Problem (0)
- Very Mild Problem (1)
- Mild or Slight Problem (2)
- Moderate Problem (3)
- Severe Problem (4)
- Problem as bad as it can be (5).

The second part has 3 questions related to frequency of use of medical products for nasal obstruction symptom relief now compared to before the procedure. Responses are on a 5-point ordered rating scale with descriptors:

- Much less frequently
- Less frequently
- About the same
- More frequently
- Much more frequently.

There is also a response of not applicable if a product was not being used prior to the procedure.

Statistical Analysis Plan TP900 (AERWAY)

The third part has 3 questions. The first is a rating on a 10-point scale of satisfaction with symptom relief following the procedure where 1 represents symptoms have no effect on daily activity and 10 being symptoms completely prevent daily activity. The second question asks if the procedure would be recommended to a friend with similar symptoms (yes or no) and the third question asks if symptoms returned would you undergo the procedure again (yes/no).

The fourth section requests information on general health, including undergoing additional nasal surgery, significant changes in health, and changes to medication regimen.

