1.0 PROTOCOL SYNOPSIS

Study Title:	A Prospective, Multicenter Study of the AER in Medical Vivaer [®] ARC Stylus for Nasal Air WAY Obstruction (AERWAY)
Device:	Vivaer [®] ARC Stylus
Device Description:	The Vivaer [®] ARC Stylus is a disposable handheld device capable of delivering bipolar radiofrequency energy to tissue.
Device Regulatory Status:	The Vivaer [®] ARC Stylus was cleared by the FDA under 510(k) #K172529 and the Aerin Console was cleared under K162810 both are also CE marked.
Study Objective:	The primary objective of this post-market study is to continue to evaluate the effectiveness of the Vivaer [®] ARC Stylus for treating the nasal valve area to improve symptoms in those diagnosed with nasal airway obstruction.
Study Design:	A Prospective, Multicenter Study of the Aerin Medical Vivaer [®] ARC Stylus for Nasal Airway Obstruction
Subject Population:	Male and female subjects who present with symptoms associated with nasal airway obstruction and meet the protocol eligibility criteria
Study Procedure:	Subjects will be followed from the Vivaer [®] treatment date out to 36 months post index procedure.
Observational Evaluation:	
• Evaluate changes in subject-reported Nasal Obstruction Symptom Evaluation (NOSE) Score.• Evaluate physicians' visual assessment of nasal airway at treatment and 3-months post index procedure• Evaluate the average anatomical Vivaer[®] treatment locations and number of placements per nostril per treatment session.• Evaluate Quality of Life questionnaire(s) at follow up timepoints to better understand improvement and pain associated with treatment over time.• Change in medication use reported at follow up timepoints in comparison to reported medications used for nasal obstruction symptoms prior to treatment.• Evaluate profile by characterizing the type and frequency of adverse events reported at or following the study procedure, and throughout the follow-up period.
Additional Evaluations:	
• Nasal treatment history• Subject Demographic information
Study Size:	Up to 125 subjects
Number of Sites:	Up to 15 sites

Study Visits: Pre-Procedure, Treatment, and 3 month follow-up

Study Subject Follow-up: 3, 6, 12, 24 and 36 months after Vivaer[®] Treatment

Study Eligibility Criteria: Inclusion Criteria:
Eligible subject will meet all the following:

1. Age 18 or older
2. Willing and able to provide informed consent

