9.1 PHASE 1: ENROLLMENT (Screening & Consent)

The treating physician or designated research staff will perform a formal evaluation of the study candidate for study eligibility, which may include a history and physical examination of the nasal area, review of overall medical history, understanding of general health and discussion of any conservative measures used for nasal airway obstruction.

The following data will be collected:

- Patient demographics
- Medical history including prior medication use, tests and treatments for nasal airway obstruction
- NOSE Score
- Treating physician pre-treatment visual assessment of the area to be treated
- Photographs/videos of each nostril will be captured

The investigator or designated staff will review all aspects of the study with the patient including the protocol, associated documents, and the follow-up process. Once the study has been explained and any questions have been answered the patient will complete and sign the Informed Consent Form (ICF).

The initial consent process as well as re-consent, when required, may take place in person or remotely (e.g., via telephone or other remote platforms such as video conferencing used in compliance with site policy) per the discretion of the investigator and with the agreement of the subject/consent designee. Whether in person or remote, the privacy and confidentiality of the subject will be maintained. The person explaining consent (and subject/consent designee, when in person) will be located in a private area (e.g., clinic consult room).

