Assessments	Prior to Nasal Valve Treatment	Nasal Valve, Treatment	Investigator Visual Assessment & subject follow-up at 3 months (+/- 2 weeks)	6, 12, 24 and 36 month Follow-ups (+/- 1 month)
Demographics and Medical History	X			
Nasal Evaluation	X	X	X	
Medication Review	X	X	X	X
Visual Assessment of Treatment Area & Photographs/videos	X	X	X	
Vivaer ARC Stylus Treatment		X		
NOSE Score	X		X	X
Visual Analog Scale (VAS)			X	
Subject QOL Questionnaire			X	X
Adverse Event Review		X	X	X
Study Exit				X*

*At 36 month visit

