Appendix A - Quality of Life Assessment

Compared to before I had the Aerin Medical Nasal procedure

	No Problem (0)	Very Mild Problem (1)	Mild or Slight Problem (2)	Moderate Problem (3)	Severe Problem (4)	Problem as bad as it can be (5)
1. Nasal obstruction						
2. Need to blow nose						
3. Sneezing						
4. Runny nose						
5. Cough						
6. Post-nasal discharge						
7. Thick nasal discharge						
8. Decreased sense of smell or taste						
9. Difficulty falling asleep						
10. Wake up at night						
11. Lack of a good night's sleep						
12. Wake up tired						
13. Fatigue						
14. Reduced productivity						
15. Reduced concentration						
16. Frustrated/restless/irritable						
17. Sad						
18. Embarrassed						
19. Snoring						
20. Mouth breathing during exercise						
21. Reduced sports or exercise tolerance						
22. Shortness of breath during experience						
23. Headache						
24. Nasal Congestion						

Statistical Analysis Plan TP900 (AERWAY)

Compared to the time prior to when you had the procedure, how often have you used each of the following products to help you with nasal congestion/difficulty breathing through your nose?

		Much less frequently	Less frequently	About the same	More Frequently	Much More Frequently
1.	Oral medications (antihistamines, oral decongestants)					
2.	Nasal sprays (nasal steroids, inhaled decongestants)					
3.	Nasal breathing strips (for example, BreatheRight® Strips)					

Rate Your Satisfaction:

1. How satisfied are you with the outcome (symptom relief) of your Vivaer Treatment (1-10)

(1 being my symptoms have no effect on my daily activity)

1 2 3 4 5 6 7 8 9 10

(10 being symptoms which completely prevent me from my daily activity)

2. Would you recommend the treatment to a friend or relative who suffered from the same nasal symptoms you had?

Yes No

3. If your symptoms were to come back would you chose to undergo the same procedure again?

Yes No

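### Part 1 of the QoL questionnaire (24 items) has no pre-treatment value and pairs a comparative heading with absolute severity answers, so it cannot support the effectiveness label it carries

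*SAP*

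**What the plan says.** **Content.** SAP 8.4 describes part 1 as 24 items rating how far various problems affect the participant's "quality of life at the time of taking the survey relative to the time prior to having the Vivaer procedure". The form in SAP Appendix A is headed "Compared to before I had the Aerin Medical Nasal procedure". The six answer columns under that heading are severity grades, scored from 0 (no problem) to 5 (the worst possible).

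**Timing.** In Protocol 9.6, Table 1, the row "Subject QOL Questionnaire" is marked at 3 months and at the 6-, 12-, 24- and 36-month follow-ups only. The screening list in Protocol 9.1 includes the NOSE score and "Medical history including prior medication use, tests and treatments for nasal airway obstruction", but not the QoL questionnaire. The treatment-visit list in 9.2 omits it too.

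**Purpose and analysis.** The protocol synopsis lists this evaluation: "Evaluate Quality of Life questionnaire(s) at follow up timepoints to better understand improvement and pain associated with treatment over time". SAP Table 1 gives the objective as "Evaluate effectiveness through participant quality of life (QoL) questionnaire feedback". The endpoint there and the analysis in SAP 9.8 are item response distributions, with means or medians where appropriate, at the five follow-up times.

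**The concern.** An effectiveness statement from a single-arm study needs a pre-treatment value, or at least a question that asks directly about change. Part 1 has neither. The heading seems meant to stand in for the missing baseline, but the answer scale gives the participant no way to report a change.

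A low item score at follow-up may therefore mean that the problem improved or that it was never there. If such scores appear in an effectiveness table, readers will tend to take them as benefit. SAP section 2 allows results to go into regulatory submissions and manuscripts. Protocol 5.0 already describes an earlier sponsor QoL survey, given at 12 to 24 months, as showing improvement in sleep, energy and productivity. The documents do not say that it was the same form, but part 1 invites the same kind of statement. Productivity, concentration, fatigue and mood are most exposed, because NOSE does not cover them.

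**Working it through.** There is no planned figure to reproduce: SAP section 5 reports no formal power analysis, and no QoL effect size is stated. The check sets the texts side by side and then works out what the data could show.

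**1. Is there a baseline?** From Protocol Table 1:

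| Assessment | Before treatment | At treatment | 3 months | 6, 12, 24, 36 months |
|---|---|---|---|---|
| NOSE | yes | no | yes | yes |
| QoL questionnaire | no | no | yes | yes |

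Protocol 9.1 and 9.2 agree with the table.

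**2. Can the answers express change?** Part 2 of the same questionnaire shows the contrast. SAP 8.4 says: "The second part has 3 questions related to frequency of use of medical products for nasal obstruction symptom relief now compared to before the procedure". Its five answers run from much less to much more often, with a midpoint for no change and a not-applicable response. Part 1 has a comparative heading but no comparative answers.

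**3. What follows if every answer means current severity?** Let m be an item mean at follow-up and b the unmeasured mean before treatment, both on the 0 to 5 scale. The change is d = m − b. With b anywhere from 0 to 5, d lies between m − 5 and m, and a negative d is improvement.

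- m = 1: d runs from 1 − 5 = −4 to 1 − 0 = +1, that is, 4 points better to 1 point worse.
- m = 2: d runs from 2 − 5 = −3 to 2 − 0 = +2, that is, 3 points better to 2 points worse.

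The width is m − (m − 5) = 5, the whole scale, whatever m is.

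**4. Does eligibility supply the missing baseline?** Let p be the share of participants who never had a given problem. With no treatment effect and stable symptoms, the share scoring 0 at follow-up is also p. The documents give no value of p for any item. The only symptom-severity threshold at entry is a NOSE score of at least 60. If the five NOSE components weigh equally (an assumption; the total runs from 0 to 100), each contributes at most 100 / 5 = 20. Three components at their maximum already give 3 × 20 = 60, so a participant could qualify with zero on two of the five, including sleep. For items outside NOSE, such as cough, sadness or embarrassment, entry guarantees nothing.

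**5. What follows if some respondents obey the heading?** A 0 could then mean no problem now, or no problem relative to before. If the two readings are mixed, current severity cannot be read cleanly either.

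**6. Extent.** 24 items × 5 follow-up times = 120 item-by-visit summaries, none of which can be tied to a pre-treatment state.

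**The case against.** The strongest reply is that the plan promises less than the criticism supposes. SAP section 2 states that no hypotheses were defined. SAP Table 1 speaks of questionnaire feedback, and the word improvement for QoL comes from the protocol synopsis. Where the SAP wants change from baseline, as for NOSE, it says so; for QoL it plans follow-up summaries only. This stands. A reader might infer that a planned change analysis cannot be carried out, but no such analysis is planned. The gap lies between the stated objective and what the data can support.

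A reader might also infer that the study's effectiveness evaluation fails. The documents do not support that. SAP 8.2 makes NOSE the primary assessment of effectiveness, it is collected before treatment, and its components include sleep and breathing during exercise. Nor is QoL the sole reason for the study: Protocol 6.0 calls sleep, productivity and concentration important to measure, but gives the purpose as evaluating additional subjects for up to 36 months.

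How respondents read the heading is unknown. SAP 8.4 also refers to the time of the survey, and the answers look like present severity. Appendix A as available lacks the not-applicable option and the fourth section described in 8.4, so fuller instructions may exist. The ambiguity should be reported as a limitation, not as proof that answers are wrong. The missing baseline does not depend on it.

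**Conclusion.** The point holds for part 1 of the questionnaire. Its post-treatment distributions and means cannot show change from before treatment for any of the 24 items at any of the five follow-up times, so they do not belong under an effectiveness objective. Under the current-severity reading, the possible change spans the full 5 points of the scale. The documents do not narrow it, since they give no item prevalences or pre-treatment scores.

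The point does not extend to NOSE or to the three product-use questions in part 2, which can show change as the participant recalls it. If respondents consistently answer for the present, part 1 can still describe the course from 3 to 36 months.

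The missing baseline and the mismatch between heading and answers are certain from the documents. How participants resolve the mismatch is not.

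**What to change.** **SAP, now.** In SAP Table 1 and 9.8, move part 1 out of the effectiveness rows. Report it descriptively as post-treatment symptom burden from 3 to 36 months. State the missing baseline and the mismatch between heading and answers as limitations, and make no claim of QoL improvement from part 1.

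**Participants already in follow-up.** Keep the heading unchanged. Rewording it midway would break comparability within the 3- to 36-month series, the one longitudinal use part 1 may still have.

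**Participants not yet treated, if any.** Add the 24 items, under a present-state heading, to the pre-treatment column of Protocol Table 1 and to section 9.1. Use the same heading at those participants' follow-up visits, and analyse change from baseline in all of them. Do not select a subgroup with high baseline item scores: in a single-arm study, regression to the mean would produce apparent improvement without any effect. This step may reach few people or none, since SAP section 3 describes the pre-treatment and 3-month visits in the past tense and Protocol 9.5 mentions subjects who exited after 24 months.

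**Cost.** For those already treated, SAP wording only. For anyone new, one more self-completed questionnaire at a visit that already collects NOSE, with their data shown separately. The QoL claim becomes weaker.
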